5.2 Exclusion Criteria

1. Subjects who are pregnant or planning to become pregnant during the study. Women of child bearing potential must have a negative pregnancy test
2. Subjects must not have received chemotherapy within 2 weeks of planned 1st day of RT.
3. No more than 3 lesions may be treated. The maximum sum of the diameter(s) of the lesion(s) must be ≤ 6 cm
4. Uncontrolled intercurrent illness including, but not limited to, ongoing or active infection (or infections requiring systemic antibiotic treatment), active upper GI ulceration or hemorrhage, symptomatic congestive heart failure, unstable angina pectoris, cardiac arrhythmia, or psychiatric illness/social situations that would in the opinion of the investigator limit compliance with study requirements

6.0 STUDY DESIGN

This is a pilot non-randomized study that will enroll patients planning to undergo treatment with SBRT for liver malignancies.

7.0 PATIENT REGISTRATION AND RECRUITMENT

Potential subjects will be identified and recruited per the recommendation of surgeons, medical oncologists, tumor boards, Department of Radiation Oncology, recommendations from outside physicians, or self-referral. No advertisement will be used to recruit subjects. Patients who appear to be eligible for this trial will undergo the Informed Consent Process and be screened for eligibility utilizing the eligibility criteria. Eligible patients who complete the Informed Consent Process will be registered in the OnCore[®] database and assigned a subject ID number. Regulatory files will be maintained by the Radiation Oncology Research Office. Applicable regulatory documents must be completed and on file prior to registration of any subjects.

8.0 STUDY PROCEDURES

8.1 Baseline

Each subject will undergo the following baseline procedures to determine eligibility within 4 weeks of registration.

1. Informed Consent
2. History and Physical
3. Vitals
4. ECOG performance status
5. Laboratory Assessments (CBC differential, platelets, CMP, INR, AFP)
6. Urine pregnancy test (for females of childbearing potential)
7. Liver severity assessments: CTP score, AJCC stage, MELD score, BCLC stage, CLIP score, ALBI score

8.2 Simulation Period

After subjects have been found eligible and enrolled to this study, each subject will undergo CT simulation for SBRT treatment planning. Two radiation treatment plans will be created for each subject and compared. The plan which best spares functional liver while maintaining adequate target coverage will be selected for each subject. Within 8 weeks of the simulation, the subject should have the following functional scans for enrollment:

1. HIDA scan
2. MRI with Eovist contrast (fMRI)

If a patient cannot obtain an MRI or refuses to undergo eovist MRI, the subject may be enrolled on the study at the discretion of the principal investigator.

8.3 Radiation Treatment Period

During radiation treatment, subjects will be seen at least once per week for clinical assessment that will include a limited physical exam and assessment of toxicity.

Midway through radiation treatment, subjects will have the following procedures:

1. Laboratory Assessments (CBC with differential, CMP, INR) for assessment of CTP, MELD, and ALBI scores.
2. HIDA scan

Subjects who have a total of 3 fractions will have Midway Assessments done after fraction 2. Subjects who have a total of 5 fractions will have Midway Assessments after fraction 3.

8.4 End of Treatment Visit

Lab assessment should be performed within 30 (+/-7) days from last radiation treatment. This includes at least CBC with diff, CMP, INR

- 1.

8.5 Follow up

Follow up visits will occur at 3, 6 and 12 months (+/-30 days) post the end of treatment visit.

Subjects will have the following procedures at this visit:

1. Physical Exam
2. Vitals
3. ECOG performance status
4. Laboratory Assessments (CBC with differential, CMP, INR +/- AFP or CEA as indicated)
5. Clinical assessment of toxicity
6. Triple-phase CT or eovist MRI
7. HIDA scan

9.0 TREATMENT PLAN

[figure not shown]
9.1 Overview

Each subject will have two radiation treatment plans created after enrollment and prior to start of radiation treatment during the simulation period. One treatment plan will follow the standard of care planning for SBRT. The second plan will incorporate functional data from the HIDA scan with the standard SBRT treatment plan. As per standard protocol, the 2 plans for a given subject will be evaluated by a dose-volume histogram to ensure SBRT constraints are met. A functional DVH will also be analyzed in order to allow a comparison of the potential relative sparing of function that the plan in which the functional data was accounted for provides.

In the HIDA-guided plan, the target will be identical and the dose to the target will not change compared with a conventionally planned SBRT plan. Tumor coverage will be equivalent between both plans. Although HIDA-guided SBRT planning may result in changes in the geometric beam arrangement and the relative weighting of beams in order to attempt to increase sparing of functional liver, HIDA-guided planning will not result in any changes to the delineated tumor target nor in the accepted level of dosimetric coverage of the tumor target itself.

[figure not shown]
The HIDA scan will be “fused” (overlaid) over the patient’s treatment planning CT, and contours that delineate areas of differing liver function will be created. The first step in contouring is the delineation of the tumor. An example of this can be found in Figure 1 below. The tumor is shown as the turquoise-colored volume in the posterior right lobe, and the liver is indicated by the dark blue contour. The HIDA scan data will then be utilized to create contours delineating areas of higher- and lower-functioning liver. The example in Figure 1 shows contours corresponding to liver function (i.e., % maximum uptake as depicted by the HIDA scan. Here, 25%-50% max (green), 50-75% max (yellow), 75-90% max (orange), 90-100% max (red). In this case, the left lobe of the patient’s liver was providing the majority of her liver function. Therefore, the HIDA scan suggests that the left lobe of the liver should be avoided, as segments 1-4 are shown to contribute more to liver function than the right lobe of the liver.

Figure 1. HIDA-guided Contouring

Once the treatment targets and avoidance structures are contoured, the treatment planning process will begin. Generally, SBRT plans use 8-10 beams arranged at various angles around the body. The use of multiple beams allows the weight of each beam to be varied in order to deliver a highly conformal radiation plan (i.e., a plan in which the prescription isodose lines closely match the target contour). Figure 2 below demonstrates a treatment plan using the HIDA data which shows that no beam would be directed at the tumor from the left anterior oblique (LAO) angle (red arrow) in order to spare the large island of functional liver tissue in the left lobe. Without the extra information provided by the HIDA scan, a non-theragnostically planned SBRT plan likely would have used a beam arrangement that did not avoid the area of functional liver tissue in question, thereby increasing the radiation dose to functional liver tissue.

Figure 2. HIDA-guided Treatment Plan

9.2 Research Imaging Protocols

1. HIDA scan
2. MRI with Eovist contrast of abdomen and pelvis

9.3 Simulation Protocol

1. Conventional or CT fluoroscopy in SBRT frame with or without abdominal compression to attempt to limit diaphragmatic motion to <1 cm.
2. CT with IV contrast (multi-phase as indicated per treating MD), supine in treatment position, 3 mm slices, per institutional protocol
3. 4D CT simulation to account for tumor motion with respiration

9.4 Radiation Planning

Standard Target Contouring guidelines

1. GTV is contoured based on CT obtained during simulation and any previous CT, MRI, or PET scans.
2. The internal target volume (ITV) will account for tumor motion as seen on 4D-CT. Viewing the lesion on individual phases may be necessary in order to adequately delineate the lesion.
3. The planning target volume (PTV) will account for set-up error and will be created by expanding the ITV 1 cm cranio-caudally and 0.5 cm radially, unless less motion can be documented on simulation scans.

Contouring from the HIDA scan

1. Based on the HIDA scan data, contours of relative functional liver will be created based on the following thresholds of maximum intensity: 0-25% maximum, 25-100% maximum, 50-100% maximum, 75-100% maximum. These structures will serve as avoidance structures in the design of radiation fields for theragnostic SBRT planning.

Standard SBRT

The standard SBRT prescription, planning, constraints, and treatment parameters are as follows:

1. Prescription:
3- or 5-fraction SBRT will be utilized in this study depending on clinical scenario. It is recommended that subjects without cirrhosis or with CTP A disease are treated with 3 fractions and those with CTP B cirrhosis are treated with 5 fractions. The dose range typically will be from 4000-5400 cGy delivered over 3-5 fractions.
2. Planning:
SBRT; IMRT if constraints not met or for additional functional sparing.

3. SBRT Constraints:

Structure	Volume	Dose / Constraint
PTV	>95%	Rx
GTV	>98%	>110% Rx
Liver – GTV	700cc or V10 Gy	<1500cGy or <70%
	1/3 uninvolved	<1000cGy (CTP-A), <1800cGy (CTP-B7)
	500cc uninvolved	<700cGy (CTP-A), <1200cGy (CTP-B7)
Duodenum	0.5 cc	2400 cGy (3 fraction) 3000 cGy (5 fraction)
	<5 cc	1650 cGy (3 fraction) 1800 cGy (5 fraction)
	<10 cc	1140 cGy (3 fraction) 1250 cGy (5 fraction)
Stomach	0.5 cc	2250 cGy (3 fraction) 3000 cGy (5 fraction)
Esophagus	0.5 cc	32 Gy (5 fx)
Spinal Cord	100%	<600cGy/fraction
Chest Wall	.5 cc	<5000cGy (5 fraction)
	<5cc	4000cGy (3 fraction)
	<30cc	3000cGy
R Kidney	2/3	<2000cGy
L kidney	1/3	<1500cGy
Heart	0.5 cc	3000 cGy (3 fraction) 5250 cGy (5 fraction)

a. Variation acceptable constraints (per RTOG 1112)

Structure	Variation acceptable	Deviation unacceptable
Esophagus max (0.5 cc)	>32 but ≤34 Gy	>34 Gy
Stomach max (0.5 cc)	>30 but ≤32 Gy	>32 Gy
Duodenum max (0.5 cc)	>30 but ≤32 Gy	>32 Gy
Small bowel max (0.5 cc)	>30 but ≤32 Gy	>32 Gy
Large bowel max (0.5 cc)	>32 but ≤34 Gy	>34 Gy
Spinal cord + 5 mm max (0.5 cc)	>25 but ≤28 Gy	>28 Gy
Kidneys: bilateral mean	>10 but ≤12 Gy	>12 Gy

4. Treatment Parameters:

- Fractionation: All subjects will have at least 48 hrs between fractions. This may be extended to weekly treatments at the treating physician's discretion.
- Image Guidance: Daily cone beam CT scan

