Currently, standard constraints for liver SBRT planning stipulate that 700 cc of “uninvolved liver”, i.e., the volume of liver minus the gross tumor volume (GTV), should receive <15 Gy. This constraint is derived from a phase I study conducted at the University of Colorado (which itself was based on surgical data showing that 75-80% of the liver can be safely resected).[9, 17] Since 25% of the assumed average liver volume of 2000 cc is 500 cc, 700 cc was used as a conservative limit. The basis for 15 Gy was that its BED is 40 Gy₃ which is less than the whole liver tolerance of 49.5 Gy₃ as determined from an early RTOG dose escalation study of whole liver RT.[18] The current constraint does not take into account the functional residual capacity of the untreated liver. However, information about regional variations in liver function could help to evaluate the safety of RT in patients who are borderline candidates for liver RT based on their liver function. In this protocol, we will meet the standard physical constraints but plan to increase safety further by attempting to decrease dose to functional areas.

The indocyanine green (ICG) retention study is presently the gold standard for assessing liver function, but this study only provides information about global liver function.[19] An ICG retention at 15 minutes (ICG15) of less than 14% has historically been used as a cutoff to select patients for major hepatectomy, but subsequent trials have shown that well-selected patients with ICG15 values above this cutoff had similar outcomes as those with lower ICG15 values[20, 21] According to the 2016 NCCN hepatobiliary guidelines, ICG15 is widely used in Asia but not in Western countries. Two studies from the University of Michigan reported baseline ICG values in patients’ pre-treatment. They reported ICG clearance as ICG half-life, whereas the surgical data looks at ICG retention at 15 minutes (ICG15). In a total of 29 patients, the values ranged from 3.75 minutes to 14.5 minutes, which would correlate with an expected ICG15 of 6.25% to 48.8%. In this study, 14 of 29 (48.3%) of patients would have had a ICG value >14%. Clearly, the patients undergoing radiation therapy for liver tumors can have a large variation in their liver function. Having more data as to what functional residual capacity correlates with the ability to safely deliver radiation therapy would be beneficial.

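### Section 9.4's two CTP-B7 liver limits carry no fraction number, so a B7 subject treated in 3 fractions keeps the same physical limits at 1.36 and 1.30 times the BED of the recommended 5

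*Combined protocol and SAP*

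**What the plan says.** Section 5.1 admits subjects with a CTP score up to 7, so B7 is the only CTP B score in the study. Section 9.4 leaves the choice of 3 or 5 fractions to the clinical scenario and adds advice by class: "It is recommended that subjects without cirrhosis or with CTP A disease are treated with 3 fractions and those with CTP B cirrhosis" with 5 (in full, "those with CTP B cirrhosis are treated with 5 fractions"). No section makes this a requirement. The usual prescription is also given without a class: "The dose range typically will be from 4000-5400 cGy delivered over 3-5 fractions".

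The constraint table in Section 9.4 has three rows for liver minus GTV:

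- A row for all classes, 700 cc or V10 Gy: "<1500cGy or <70" (the second figure is a percentage).
- One third of uninvolved liver: "<1000cGy (CTP-A), <1800cGy (CTP-B7".
- 500 cc of uninvolved liver: "<700cGy (CTP-A), <1200cGy (CTP-B7".

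The last two rows are set by CTP class and give no fraction number. The duodenum, stomach and heart rows do give separate limits, always lower for 3 fractions; for 0.5 cc of duodenum the entry is "2400 cGy (3 fraction) 3000 cGy (5 fraction". Some other rows (the all-class liver row, the kidneys, 30 cc of chest wall) also lack a fraction number. The table of acceptable variations has no liver row.

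**The concern.** A physical dose limit means different things in 3 and in 5 fractions, because the same total in fewer, larger fractions has more effect on normal tissue. The table applies this to the duodenum, stomach and heart but not to the two class-specific liver rows. A B7 subject treated in 3 fractions, against the advice but within the protocol, would be planned to the same 18 and 12 Gy as one treated in 5.

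At stake is the safety margin for the class with the poorer liver function. These limits act before dose is given. The monitoring in Section 11 acts afterwards, and Section 2.0 notes that no standard way of reversing radiation-induced liver disease is known and that it can be fatal.

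**Working it through.** **Inputs.** B7 limits 18 and 12 Gy, CTP-A limits 10 and 7 Gy, and the all-class row, all from Section 9.4. From Section 2.0: a BED of 40 Gy3 for 15 Gy, a whole-liver tolerance of 49.5 Gy3, and an average liver of 2000 cc ("Since 25% of the assumed average liver volume of 2000 cc is 500 cc, 700 cc was used as a conservative limit"). From Section 5.2: lesion diameters summing to at most 6 cm.

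**Formula.** BED = D × (1 + (D/n)/3), with total dose D, n fractions and alpha/beta = 3 Gy, as the Gy3 notation implies.

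**The plan's own figure.** 15 Gy in 3: 15 × (1 + 5/3) = 40.0 Gy3, as stated. In 5 fractions it would be 30.0, so the stated value is a 3-fraction one.

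**Effect of the fraction number on the B7 limits.**

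| B7 limit | 5 fractions | 3 fractions | Ratio |
|---|---|---|---|
| 1/3 uninvolved, 18 Gy | 18 × (1 + 3.6/3) = 39.6 | 18 × (1 + 6/3) = 54.0 | 1.36 |
| 500 cc, 12 Gy | 12 × (1 + 2.4/3) = 21.6 | 12 × (1 + 4/3) = 28.0 | 1.30 |

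At alpha/beta 2 the ratios are 72.0/50.4 = 1.43 and 36.0/26.4 = 1.36. At alpha/beta 4 they are 45.0/34.2 = 1.32 and 24.0/19.2 = 1.25.

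**Difference between classes on the recommended schedules (A in 3, B7 in 5).** A: 10 Gy gives 21.1 and 7 Gy gives 12.4 Gy3. B7 against A: 39.6/21.1 = 1.88 and 21.6/12.4 = 1.74. The B7 limits are therefore looser even when the advice is followed.

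**Equal-BED 3-fraction limits, if the B7 limits are meant for 5.** Solve x + x²/9 = BED, so x = 4.5 × (−1 + √(1 + 4·BED/9)).

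- 39.6 Gy3: 4.5 × (−1 + √18.6) = 14.9 Gy.
- 21.6 Gy3: 4.5 × (−1 + √10.6) = 10.15, about 10.2 Gy.

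**What the all-class row leaves, in 3 fractions at 2000 cc.**

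- *700 cc option.* One third is 667 cc, less than 700 cc, so it is already held below 15 Gy and the 18 Gy row does not bind. It binds only above 3 × 700 = 2100 cc. At one third the comparison is 15 against 14.9 Gy, practically nil. The 500 cc row still binds, at 12 against 10.2 Gy.
- *V10 option.* At least 30% (600 cc) is at or below 10 Gy. That covers the 500 cc, for any liver of 1667 cc or more, at a dose just under the equal-BED 10.15 Gy. The 18 Gy row governs only 33.3% − 30% = 3.3% of the volume, about 67 cc.

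Removing the largest single lesion allowed (a 6 cm sphere, π/6 × 6³ = 113 cc) leaves 1887 cc, with one third = 629 cc and 30% = 566 cc. The same rows bind.

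**The case against.** The strongest reply is that little remains to fix. Section 9.4 pairs CTP A with 3 fractions and CTP B with 5 in one sentence, so a planner can infer which schedule each limit belongs to, and the problem arises only if a physician departs from that advice. Section 2.0 treats 700 cc below 15 Gy as the standard constraint and says that it will be met. In 3 fractions at 2000 cc that leaves 40.0 Gy3 at one third and 28.0 Gy3 at 500 cc, neither above the 40 Gy3 which that section accepts. Selection of the better-sparing plan (8.2), mid-treatment laboratory tests (8.3), suspension for new ascites or encephalopathy (11.0) and monthly safety review (16.0) give further protection.

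Most of this stands, and it is why the point is minor. It does not close the gap: the schedule is advice, the V10 option may replace the 700 cc one, and the 500 cc row still lacks a 3-fraction value.

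Three stronger readings are tempting, and the documents do not support them:

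- A reader might infer that the missing fraction number is what gives B7 looser limits than CTP A. It is not. The difference is there on the recommended schedules (1.88 and 1.74 times) and appears to be a deliberate choice by class.
- A reader might set 54.0 Gy3 against the 49.5 Gy3 tolerance and call the limit unsafe. The 49.5 is a whole-liver figure and the 18 Gy limit concerns one third of the uninvolved liver. On the 700 cc option, 54.0 is also not reached at one third in a liver of up to 2100 cc.
- A reader might cite the statement in Section 2.0 that 42 Gy in 3 fractions was unsafe in CTP B. That is a prescription dose, not a spared-liver limit, and the patients with progressive liver dysfunction were B8 or worse, who are ineligible here.

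**Conclusion.** The point holds as a minor safety clarification. On a schedule that the protocol permits but does not recommend, the two B7 liver limits allow 1.36 and 1.30 times the BED that they allow in 5 fractions. After the all-class row, at 2000 cc, the part due to fraction number is 12 against about 10.2 Gy on 500 cc, or about 67 cc of liver, depending on which option of that row is used.

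This rests on the linear-quadratic model with alpha/beta 3 (the direction is the same from 2 to 4) and on the assumed 2000 cc liver. That the B7 limits were written for 5 fractions is an inference from the recommendation and from 39.6 lying close to the 40 Gy3 in Section 2.0; the documents do not say so. They also do not say how many of the 20 subjects would be B7 or how many of those would be treated in 3 fractions.

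The primary endpoint compares two plans with the same target and target dose in the same subject, so it is unaffected. So are the sample size and the 3-of-15 rule.

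**What to change.** In the Section 9.4 table, label the 18 Gy and 12 Gy entries *(CTP-B7, 5 fractions)*. Then do one of the following:

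1. Require 5 fractions for CTP-B7 subjects.
2. Add lower 3-fraction limits for CTP-B7, in the form already used for the duodenum, stomach and heart. The equal-BED values are about 14.9 Gy for one third and 10.2 Gy for 500 cc; the investigators should confirm or replace them.

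Holding a B7 subject in 3 fractions to the CTP-A limits of 10 and 7 Gy would be stricter than equal BED, and the documents give no basis for it. Neither option changes the limits on the recommended schedules.

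The cost is two labels and either one sentence or two table entries. The downside is less physician discretion and up to two more treatment sessions for a B7 subject who would otherwise have had 3 fractions. No extra subjects or study procedures are needed.

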11.0 TOXICITIES TO BE MONITORED/DOSAGE MODIFICATIONS

All subjects will have laboratory evaluation prior to initiation of treatment. This includes CBC with differential, platelets, CMP, and INR.. Radiation treatment will be suspended in subjects who develop new ascites (as indicated by abdominal ultrasound, CT scan, or physical exam) or encephalopathy. If the patient's clinical status is borderline and the treating physician determines a treatment break is necessary, re-evaluation for further treatment can occur 1-2 days later.

	CTP-A	CTP-B7
Total Bilirubin	<3	<4
Albumin	>2.5	>2.5
INR	<1.5X upper normal	PT > 6 seconds above normal
ANC	>1000	>1000
Platelets	>50,000	>50,000
Hgb	>9	>9
Ascites	none	none
Encephalopathy	none	none

The subject will be seen at least once weekly during treatment for assessment of side effects. The most current version of Common Terminology Criteria for Adverse Events (CTCAE) will be used for grading toxicity.

For the purposes of this study, we will monitor the following:

- Labs: AST, ALT, Alkaline phosphatase, bilirubin, INR, platelets, albumin, lymphocytes, sodium
- Hepatobiliary disorders: hepatic failure, hepatic hemorrhage, hepatic necrosis, hepatic pain, perforation of bile duct, portal hypertension, portal vein thrombosis, bile duct stenosis, biliary fistula, cholecystitis, gallbladder fistula
- Gastrointestinal disorders: ascites, duodenal hemorrhage, duodenal obstruction, duodenal perforation, duodenal stenosis, duodenal ulcer, gastric necrosis, gastric perforation, gastric stenosis, gastric ulcer
- Nervous system disorders: encephalopathy
- Musculoskeletal and connective tissue disorders: chestwall pain
- Renal and urinary disorders: acute kidney injury

A copy of the most current CTCAE version is available at <http://ctep.cancer.gov/reporting/>

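### The 0.5 cc heart limits in section 9.4 conflict: 5 fractions allow 10.5 Gy each, 3 fractions only 10.0 Gy; check both against their source

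*Combined protocol and SAP*

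**What the plan says.** The SBRT constraint table in section 9.4 gives the heart one row, for 0.5 cc: "3000 cGy (3 fraction) 5250 cGy (5 fraction"). It cites no source for either figure.

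Four other rows pair a 3-fraction and a 5-fraction limit for the same volume:
- duodenum 0.5 cc: "2400 cGy (3 fraction) 3000 cGy (5 fraction")
- duodenum 5 cc: "1650 cGy (3 fraction) 1800 cGy (5 fraction")
- duodenum 10 cc: "1140 cGy (3 fraction) 1250 cGy (5 fraction")
- stomach 0.5 cc: "2250 cGy (3 fraction) 3000 cGy (5 fraction")

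The chest wall rows are not a pair, because their volumes differ.

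The minimum interval is the same for both schedules: "All subjects will have at least 48 hrs between fractions". Weekly treatment is allowed at the physician's discretion and is not tied to the number of fractions. The prescription is typically 40 to 54 Gy over 3 to 5 fractions, and 5 fractions are recommended for CTP B disease. Section 9.1 makes the table the test for both of a subject's plans: "the 2 plans for a given subject will be evaluated by a dose-volume histogram to ensure SBRT constraints are met".

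The variation table in section 9.4 has no heart row. The list that section 11.0 introduces with "For the purposes of this study, we will monitor the following" has no cardiac item.

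**The concern.** Spreading a dose over more fractions normally goes with a higher total and a smaller dose in each fraction. The heart row raises both the total and the dose per fraction, so its two limits cannot express the same tolerance.

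In practice the row can rank plans the wrong way round. A 5-fraction plan giving 0.5 cc of heart 50 Gy passes, and a 3-fraction plan giving 31 Gy fails, although the first delivers the larger dose in total and nearly the same dose per fraction (10.0 against 10.3 Gy).

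The 5-fraction limit is also weak as a screen. It lies above every prescription below 52.5 Gy. For prescriptions up to 47.7 Gy (52.5/1.10) it lies above even the 110% of prescription required in the GTV. Nothing else in the protocol limits heart dose at planning. If 30 Gy is the wrong figure instead, 3-fraction plans near the heart are held tighter than intended.

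**Working it through.** **Inputs.** All limits are from the section 9.4 table, in Gy. Equal dose per fraction is assumed.

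**Step 1: check without a model.** Compare three fractions at the 5-fraction limit, 3 × (D5/5), with the 3-fraction limit D3.

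| Row | D3 | D5 | Per fraction, 3 → 5 | 3 × D5/5 against D3 |
|---|---|---|---|---|
| Duodenum 0.5 cc | 24 | 30 | 8.0 → 6.0 | 18.0 < 24 |
| Duodenum 5 cc | 16.5 | 18 | 5.5 → 3.6 | 10.8 < 16.5 |
| Duodenum 10 cc | 11.4 | 12.5 | 3.8 → 2.5 | 7.5 < 11.4 |
| Stomach 0.5 cc | 22.5 | 30 | 7.5 → 6.0 | 18.0 < 22.5 |
| Heart 0.5 cc | 30 | 52.5 | 10.0 → 10.5 | **31.5 > 30** |

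Only heart fails. Two more fractions (2 × 10.5 = 21 Gy) follow. The highest 5-fraction limit that passes against 30 Gy in 3 is 30 × 5/3 = 50 Gy.

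**Step 2: size of the gap.** Use the linear-quadratic (LQ) form BED = D(1 + D/(n·α/β)). It reproduces the protocol's own figure in section 2.0: 15 Gy in 3 fractions at α/β 3 gives 15(1 + 5/3) = 40 Gy3. The protocol uses α/β 3 for liver; using it for heart is an assumption, so ranges are shown.

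- Heart, 30 Gy in 3: 30(1 + 10/3) = 130 Gy3.
- Heart, 52.5 Gy in 5: 52.5(1 + 10.5/3) = 236 Gy3. The ratio is 1.82.
- Bounds on that ratio: 52.5/30 = 1.75 for very large α/β, and (52.5²/5)/(30²/3) = 1.84 for very small α/β. No α/β reconciles the pair.
- The same ratio at α/β 3 for the other rows: duodenum 90.0/88.0 = 1.02, 39.6/46.75 = 0.85 and 22.9/25.8 = 0.89; stomach 90.0/78.75 = 1.14.
- The two plans named above: 50 Gy in 5 is 50(1 + 10/3) = 217 Gy3; 31 Gy in 3 is 31(1 + 10.33/3) = 138 Gy3. The ratio is 1.57.

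**Step 3: LQ equivalents, for illustration.** Solve for D: D = (n·α/β/2)(−1 + √(1 + 4·BED/(n·α/β))).

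| α/β | 30 Gy in 3, given in 5 | 52.5 Gy in 5, given in 3 |
|---|---|---|
| 1 | 38.2 | 41.1 |
| 3 | 37.3 | 41.8 |
| 10 | 35.2 | 43.8 |

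The first column can never exceed 30√(5/3) = 38.7 Gy. If 52.5 Gy is the correct cell, the 3-fraction limit is about 12 Gy tighter than it implies (41.8 − 30).

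**The case against.** The protocol never says that paired limits are iso-effective, and the two heart figures may come from different sources. The stomach pair misses LQ equivalence too: its 5-fraction limit is 30 Gy, while the LQ equivalent of 22.5 Gy in 3 cannot exceed 22.5√(5/3) = 29.05 Gy. Exposure may also be small. Lesion diameters may sum to at most 6 cm, uncontrolled symptomatic heart failure, unstable angina and arrhythmia are exclusions (section 5.2), and subjects are assessed at least weekly during treatment (section 8.3). The 40 to 54 Gy range covers both schedules, so how often the 5-fraction limit would bind is not known.

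Much of this stands. It confines LQ to showing size and keeps the clinical risk modest. It does not remove the conflict in step 1, which uses neither iso-effectiveness nor α/β. Equal minimum spacing does not explain it either. Clinical assessment during treatment also comes after some of the dose has been given.

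A reader might infer that 52.5 Gy is the error and that the table should carry a 37 Gy cap at once. The documents do not support that step:
- Nothing shows that the 30 Gy cell is the correct one. The comparator rows cover only duodenum and stomach; they flag an anomaly but say nothing about heart tolerance.
- The move from 50 to 37 Gy rests wholly on LQ and an assumed α/β.
- A band of 35 to 38 Gy would not be safe by its own logic. At α/β 3, 38 Gy in 5 gives 38(1 + 7.6/3) = 134.3 Gy3, looser than the 130 Gy3 it should match.
- 37 Gy is below every typical prescription. Where the target overlaps the heart, such a cap could force a loss of coverage on the strength of an unverified figure. That trade-off is clinical.

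**Conclusion.** The heart pair is internally inconsistent and should be corrected. At equal dose per fraction, three fractions at the 5-fraction limit exceed the 3-fraction limit by 1.5 Gy, with 21 Gy still to come. The BED ratio is 1.75 to 1.84 at any α/β under LQ. The documents do not show which cell is wrong. No stated calculation fails; this is an unsourced and conflicting constraint.

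A reader might also infer that the trial's result is at risk or that cardiac harm is likely. Neither follows. The primary endpoint, sample size and analysis are unaffected. The documents do not say how many subjects have tumours near the heart and receive 5 fractions. Enrolment is 20, eligibility stops at CTP 7 and 5 fractions are recommended mainly for CTP B, so the number is probably small and may be zero.

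**What to change.** 1. Check both heart figures against their source, cite it in the table and amend the incorrect cell.
2. Until that is done, the treating physician and physics team review and document any 5-fraction plan whose 0.5 cc heart dose exceeds what the 3-fraction limit supports. Two reference marks help. A dose above 50 Gy conflicts with 30 Gy in 3 without any model. The LQ equivalent of 30 Gy in 3 is about 37 Gy at α/β 3 (35 to 38 Gy for α/β 10 to 1), as an illustration and not as a protocol limit.
3. If 52.5 Gy is confirmed, keep it and re-examine the 3-fraction limit instead (LQ equivalent about 42 Gy).

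The cost is one source lookup, one table amendment with the IRB approval that section 15.0 requires, and interim review of the few plans near the heart.
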